History of malignancy (non-metastatic and metastatic; excluding non- melanoma skin cancer)	Outcome: VTE risk factor	Defined as ≥1 ICD-10 diagnosis code for malignancy (excluding non-melanoma skin cancer) in the 12 months prior to or on the day of the index tofacitinib dispensing.
Age >50 years at tofacitinib initiation	Outcome: VTE risk factor	Defined as age at tofacitinib initiation >50 years.
History of diabetes	Outcome: VTE risk factor	Defined as $\geq 1$ ICD-10 diagnosis code for diabetes in the 12 months prior to or on the day of the index tofacitinib dispensing.
History of hypertension	Outcome: VTE risk factor	Defined as ≥1 ICD-10 diagnosis code for hypertension in the 12 months prior to or on the day of the index tofacitinib dispensing.
Initiating tofacitinib with ≥1 VTE risk factor	Outcome: VTE risk factor	Defined as ≥1 VTE risk factor (as listed and defined above) identified in the 12 months prior to or on the day of the index tofacitinib dispensing (unless otherwise specified).
Number of VTE risk factors identified prior to tofacitinib initiation	Outcome: VTE risk factor	Calculated as the sum of the number of VTE risk factors (as listed and defined above) identified in the 12 months prior to or on the day of the index tofacitinib dispensing (unless otherwise specified).

Table 3.	Operational	definitions of	f study	variables in	the selected	databases
----------	-------------	----------------	---------	--------------	--------------	-----------

Variable	Role	Operational definition
Number of UC patients with: ≥1 VTE risk factor; no prior alternative therapy (i.e., biologic); and an ADD >10 mg in Weeks 16-23, Weeks 24- 31, Weeks 32-39, and Weeks 40-47 of follow-up t	Outcome: VTE risk factor	Defined as a patient meeting all of the following criteria: ≥1 ICD-10 diagnosis code for UC; ≥1 VTE risk factor (as listed and defined above); 0 prescription medication dispensings for a biologic (as identified by ATC codes) in the 12 months prior to and including the date of the index tofacitinib prescription dispensing; and an ADD of >10 mg in Weeks 16-23, Weeks 24-31, Weeks 32- 39, and Weeks 40-47 of follow-up, respectively (ADD defined in Section 9.3.4). Complete list of biologics in ANNEX 6. LIST OF ATC CODES FOR MEDICATIONS OF INTEREST TO AVOID WHILE TAKING TOFACITINIB.

 Table 3.
 Operational definitions of study variables in the selected databases

Assessment of VTE risk factors while receiving tofacitinib therapy (duration of tofacitinib therapy defined in Section 9.3.3)

VTE	Outcome: VTE risk factor	Defined as $\geq 1$ ICD-10 diagnosis code for VTE while receiving tofacitinib therapy.
Surgery, major	Outcome: VTE risk factor	Defined as $\geq 1$ procedure code for a major surgery while receiving tofacitinib therapy.
MI	Outcome: VTE risk factor	Defined as $\geq$ 1 ICD-10 diagnosis code for an MI while receiving tofacitinib therapy.
Heart failure	Outcome: VTE risk factor	Defined as $\geq$ 1 ICD-10 diagnosis code for heart failure while receiving tofacitinib therapy.
Use of combined hormonal contraceptives or hormonal replacement therapy	Outcome: VTE risk factor	Defined as ≥1 prescription dispensing of a combined hormonal contraceptives and/or hormonal replacement therapy (as identified by ATC codes) while receiving tofacitinib therapy.
Inherited coagulation disorder	Outcome: VTE risk factor	Defined as ≥1 ICD-10 diagnosis code for inherited coagulation disorder while receiving tofacitinib therapy.
Malignancy (non- metastatic and metastatic; excluding non-melanoma skin cancer)	Outcome: VTE risk factor	Defined as ≥1 ICD-10 diagnosis code for malignancy (excluding non-melanoma skin cancer) while receiving tofacitinib therapy.
Diabetes	Outcome: VTE risk factor	Defined as ≥1 ICD-10 diagnosis code for diabetes while receiving tofacitinib therapy.

Variable	Role	Operational definition
Hypertension	Outcome: VTE risk factor	Defined as ≥1 ICD-10 diagnosis code for hypertension while receiving tofacitinib therapy.
Discontinuation of tofacitinib after developing ≥1 VTE risk factors while taking tofacitinib	Outcome: VTE risk factor	Defined as ≥1 VTE risk factor while receiving tofacitinib therapy (as listed and defined above) PLUS 0 prescription dispensings for tofacitinib within a specific time window after the code for the VTE risk factor.
		Note: The time window for when to look for a tofacitinib prescription dispensing will be specific to the VTE risk factor acquired while receiving tofacitinib therapy and will be operationalized during SAP development.
		Duration of tofacitinib therapy defined in Section 9.3.3.
Continuation of tofacitinib after developing ≥1 VTE risk factors while taking tofacitinib	Outcome: VTE risk factor	Defined as $\geq 1$ VTE risk factor while receiving tofacitinib therapy (as listed and defined above) PLUS $\geq 1$ prescription dispensing for tofacitinib within a specific time window after the code for the VTE risk factor.
		Note: The time window for when to look for a tofacitinib prescription dispensing will be specific to the VTE risk factor acquired while receiving tofacitinib therapy and will be operationalized during SAP development.
		Duration of tofacitinib therapy defined in Section 9.3.3.
Compliance to recommend	lations for limitations of use in patie	nts aged 65 years and older
Initiating tofacitinib with no prior use of an alternative therapy (i.e., biologic) among patients 65 years of age and older	Outcome: Age 65 years and older	Defined as patients who are 65 years and older on the date of the index tofacitinib dispensing with 0 prescription dispensings for a biologic (as identified by ATC codes) in the 12 months prior.
		Complete list of biologics in ANNEX 6. LIST OF ATC CODES FOR MEDICATIONS OF INTEREST TO AVOID WHILE TAKING TOFACITINIB.

Table 3.	Operational	definitions of	fstudy	variables in	the selected	databases
----------	-------------	----------------	--------	--------------	--------------	-----------

Variable	Role	Operational definition
Discontinuation of tofacitinib for patients who turn 65 years old while receiving tofacitinib	Outcome: Age 65 years and older	Defined as patients aged 65 years, receiving tofacitinib, who have 0 prescription dispensings of tofacitinib from the time they turn 65.5 years old through to the end of the follow-up period.
		Note: Patients have 6 months to discontinue tofacitinib to allow them time to be seen by their healthcare provider.
		Duration of tofacitinib therapy defined in Section 9.3.3.
Inappropriate continuation of tofacitinib for patients who turn 65 years old while receiving tofacitinib	Outcome: Age 65 years and older	Defined as patients aged 65 years, receiving tofacitinib, who have $\geq 1$ prescription dispensing of tofacitinib from the time they turn 65.5 years old through to the end of the follow-up period and 0 prescription dispensings for a biologic (as identified by ATC codes) prior to that tofacitinib prescription dispensing.
		Complete list of biologics in ANNEX 6. LIST OF ATC CODES FOR MEDICATIONS OF INTEREST TO AVOID WHILE TAKING TOFACITINIB.
		Note: Patients have 6 months to discontinue tofacitinib to allow them time to be seen by their healthcare provider.
		Duration of tofacitinib therapy defined in Section 9.3.3.

 Table 3.
 Operational definitions of study variables in the selected databases

Variable	Role	Operational definition		
Appropriate continuation of tofacitinib for patients who turn 65 years old while receiving tofacitinib	Outcome: Age 65 years and older	Defined as patients aged 65 years, receiving tofacitinib, who have $\geq 1$ prescription dispensing of tofacitinib from the time they turn 65.5 years old through to the end of the follow-up period PLUS $\geq 1$ prescription dispensing for a biologic (as identified by ATC codes) prior to that tofacitinib prescription dispensing.		
		Complete list of biologics in ANNEX 6. LIST OF ATC CODES FOR MEDICATIONS OF INTEREST TO AVOID WHILE TAKING TOFACITINIB.		
		Note: Patients have 6 months to discontinue tofacitinib to allow them time to be seen by their healthcare provider.		
		Duration of tofacitinib therapy defined in Section 9.3.3.		
Analysis of CV risk factors	Analysis of CV risk factors in patients using tofacitinib w			
Assessment of CV risk factor 9.7.1.2.2.1.3 [Patients with	rs prior to initiation of tofacitinib (will CV risk factors])	be stratified by sex as outlined in Section		
Elderly at tofacitinib initiation (patients 65 years and older)	Outcome: CV risk factor	Calculated as the date of tofacitinib initiation minus the patient's year of birth and reported in the following categories: $<65$ years and $\ge 65$ years.		
Current or past smoker x	Outcome: CV risk factor	Defined as $\geq 1$ ICD-10 diagnosis code for tobacco use disorder or $\geq 1$ procedure code for counselling visits for smoking or $\geq 1$ prescription dispensing (as identified by ATC code[s]) for a nicotine replacement product in the 12 months prior to or on the day of the index tofacitinib dispensing.		
History of diabetes	Outcome: CV risk factor	Defined as ≥1 ICD-10 diagnosis code for diabetes in the 12 months prior to or on the day of the index tofacitinib dispensing.		

Table 3.Operational definitions of study	variables in the selected databases
--	-------------------------------------

<sup>w In GKV claims, outpatient diagnoses are reported quarterly.

<sup>x Potential for very low sensitivity leading to misclassification. This variable will be reported if feasible.

Variable	Role	Operational definition
History of hypertension	Outcome: CV risk factor	Defined as $\geq 1$ ICD-10 diagnosis code for hypertension or $\geq 1$ prescription dispensing (as identified by ATC code[s]) for an antihypertensive in the 12 months prior to or on the day of the index tofacitinib dispensing.
		Complete list in ANNEX 8. LIST OF ATC CODES FOR ANTIHYPERTENSIVES.
History of hyperlipidaemia	Outcome: CV risk factor	Defined as $\geq 1$ ICD-10 diagnosis code for hyperlipidaemia or $\geq 1$ prescription dispensing (as identified by ATC code[s]) for a statin or other antihyperlipidaemic in the 12 months prior to or on the day of the index tofacitinib dispensing.
		Complete list in ANNEX 9. LIST OF ATC CODES FOR ANTIHYPERLIPIDAEMICS.
History of coronary artery disease (defined as MI, stroke, CABG [coronary artery bypass graft], or PCI [percutaneous coronary intervention])	Outcome: CV risk factor	Defined as $\geq 1$ ICD-10 diagnosis code for MI or stroke or $\geq 1$ procedure code for CABG or PCI in the 12 months prior to or on the day of the index tofacitinib dispensing.
History of chronic kidney disease	Outcome: CV risk factor	Defined as $\geq 1$ ICD-10 diagnosis code for chronic kidney disease in the 12 months prior to or on the day of the index tofacitinib dispensing.
History of stable angina pectoris	Outcome: CV risk factor	Defined as ≥1 ICD-10 diagnosis code for stable angina pectoris in the 12 months prior to or on the day of the index tofacitinib dispensing.
Initiating tofacitinib with $\geq 1$ CV risk factor	Outcome: CV risk factor	Defined as ≥1 CV risk factor (as listed and defined above) identified in the 12 months prior to or on the day of the index tofacitinib dispensing.

 Table 3.
 Operational definitions of study variables in the selected databases

Variable	Role	Operational definition
Initiating tofacitinib with ≥1 CV risk factor and no prior use of an alternative therapy (i.e., biologic)	Outcome: CV risk factor	
 
Defined as ≥1 CV risk factor (as listed and defined above) identified in the 12 months prior to or on the day of the index tofacitinib dispensing—AND—0 prescription medication dispensings for a biologic (as identified by ATC code) in the 12 months prior to and including the date of the index tofacitinib prescription dispensing.
 
Complete list of biologics in ANNEX 6. LIST OF ATC CODES FOR MEDICATIONS OF INTEREST TO AVOID WHILE TAKING TOFACITINIB.
 

 Table 3.
 Operational definitions of study variables in the selected databases

Assessment of CV risk factors while receiving tofacitinib therapy (duration of tofacitinib therapy defined in Section 9.3.3) (will be stratified by sex as outlined in Section 9.7.1.2.2.1.3 [Patients with CV risk factors])

Elderly (patients 65 years and older)	Outcome: CV risk factor	Defined as patients aged 65 years or older while receiving tofacitinib.
Current smoker x	Outcome: CV risk factor	Defined as $\geq 1$ ICD-10 diagnosis code for tobacco use disorder or $\geq 1$ procedure code for counselling visits for smoking or $\geq 1$ prescription dispensing (as identified by ATC code[s]) for a nicotine replacement product while receiving tofacitinib.
Diabetes	Outcome: CV risk factor	Defined as ≥1 ICD-10 diagnosis code for diabetes while receiving tofacitinib therapy.
Hypertension	Outcome: CV risk factor	Defined as ≥1 ICD-10 diagnosis code for hypertension or ≥1 prescription dispensing (as identified by ATC code[s]) for an antihypertensive while receiving tofacitinib. Complete list in ANNEX 8. LIST OF ATC CODES FOR
		ANTIHYPERTENSIVES.
Hyperlipidaemia	Outcome: CV risk factor	Defined as $\geq 1$ ICD-10 diagnosis code for hyperlipidaemia or $\geq 1$ prescription dispensing (as identified by ATC code[s]) for a statin or other antihyperlipidaemic while receiving tofacitinib.
		Complete list in ANNEX 9. LIST OF ATC CODES FOR ANTIHYPERLIPIDAEMICS.

Variable	Role	Operational definition
Coronary artery disease (defined as MI, stroke, CABG [coronary artery bypass graft], or PCI [percutaneous coronary intervention])	Outcome: CV risk factor	Defined as ≥1 ICD-10 diagnosis code for MI or stroke or ≥1 procedure code for CABG or PCI while receiving tofacitinib therapy.
Chronic kidney disease	Outcome: CV risk factor	Defined as ≥1 ICD-10 diagnosis code for chronic kidney disease while receiving tofacitinib.
Stable angina pectoris	Outcome: CV risk factor	Defined as ≥1 ICD-10 diagnosis code for stable angina pectoris while receiving tofacitinib.
Discontinuation of tofacitinib after developing ≥1 CV risk factors while taking tofacitinib	Outcome: CV risk factor	Defined as ≥1 CV risk factor while receiving tofacitinib therapy (as listed and defined above) PLUS 0 prescription dispensings for tofacitinib within a specific time window after the code for the CV risk factor.
		Note: The time window for when to look for a tofacitinib prescription dispensing will be specific to the CV risk factor acquired while receiving tofacitinib therapy and will be operationalized during SAP development.
		Duration of tofacitinib therapy defined in Section 9.3.3.
Continuation of tofacitinib after developing ≥1 CV risk factors while taking tofacitinib	Outcome: CV risk factor	Defined as $\geq 1$ CV risk factor while receiving tofacitinib therapy (as listed and defined above) PLUS $\geq 1$ prescription dispensing for tofacitinib within a specific time window after the code for the CV risk factor.
		Note: The time window for when to look for a tofacitinib prescription dispensing will be specific to the CV risk factor acquired while receiving tofacitinib therapy and will be operationalized during SAP development.
		Duration of tofacitinib therapy defined in Section 9.3.3.

 Table 3.
 Operational definitions of study variables in the selected databases

Variable	Role	Operational definition	
Analysis of malignancy ris	Analysis of malignancy risk factors in patients using tofacitinib y		
Assessment of malignancy re	Assessment of malignancy risk factors prior to initiation of tofacitinib		
Elderly at tofacitinib initiation (patients 65 years and older)	Outcome: Malignancy risk factor	Calculated as the date of tofacitinib initiation minus the patient's year of birth and reported in the following categories: $<65$ years and $\geq 65$ years.	
History of malignancy (non-metastatic and metastatic, excluding non- melanoma skin cancer)	Outcome: Malignancy risk factor	Defined as ≥1 ICD-10 diagnosis code for a malignancy (excluding non-melanoma skin cancer) in the 12 months prior to or on the day of the index tofacitinib dispensing.	
Current or past smoker x	Outcome: Malignancy risk factor	Defined as $\geq 1$ ICD-10 diagnosis code for tobacco use disorder or $\geq 1$ procedure code for counselling visits for smoking or $\geq 1$ prescription dispensing (as identified by ATC code[s]) for a nicotine replacement product in the 12 months prior to or on the day of the index tofacitinib dispensing.	
Initiating tofacitinib with ≥1 malignancy risk factor	Outcome: Malignancy risk factor	Defined as ≥1 malignancy risk factor (as listed and defined above) identified in the 12 months prior to or on the day of the index tofacitinib dispensing.	
Initiating tofacitinib with ≥1 malignancy risk factor and no prior use of an alternative therapy (i.e., biologic)	Outcome: Malignancy risk factor	Defined as ≥1 malignancy risk factor (as listed and defined above) identified in the 12 months prior to or on the day of the index tofacitinib dispensing—AND— 0 prescription medication dispensings for a biologic (as identified by ATC code) in the 12 months prior to and including the date of the index tofacitinib prescription dispensing.	
		Complete list of biologics in ANNEX 6. LIST OF ATC CODES FOR MEDICATIONS OF INTEREST TO AVOID WHILE TAKING TOFACITINIB	
Assessment of malignancy risk factors while receiving tofacitinib therapy (duration of tofacitinib therapy defined in Section 9.3.3)			

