#### Figure 1. Overview of the study observation period

### 9.2.1. VTE Reporting Periods

A 105-month **observation period** will begin 01 April 2016 and end 31 December 2024. An 81-month **indexing period** will begin 01 April 2017 (i.e., the earliest date of the full distribution of the original aRMM materials for a country and indication [Sweden, RA]), end 31 December 2023, and be used to identify patients with  $\geq$ 1 tofacitinib prescription dispensing. Additionally, for some analyses, the indexing period will be split into the following 3 periods:

• **Reporting Period 1**, which will cover the up-to-26-month period after the initial distribution of the aRMM materials but *prior to* the PRAC/CHMP's notification of an increased risk of VTE among patients already at high risk (01 April 2017 through 31 May 2019, to allow for dissemination of DHPC letters following announcement of the provisional measures);

**Note:** Hungary will not have a **Reporting Period 1** because it received full reimbursement for RA in May 2019 and has yet to receive full reimbursement for PsA and UC (anticipated Q1 2023).

• **Reporting Period 2**, which will cover the 16-month period of and after the PRAC/CHMP's notification of an increased risk of VTE and mortality, through initial distribution and uptake of the 2019 Article 20 referral aRMM materials (1 June 2019 through 30 September 2020); and

**Note:** Hungary will not have a **Reporting Period 2** for PsA and UC because the September 2020 distribution date for the 2019 Article 20 referral aRMM materials in Hungary occurred prior to PsA and UC receiving full reimbursement (anticipated Q1 2023). Additionally, **Reporting Period 2** for RA in Hungary will only allow for <1 month of uptake of the 2019 Article 20 referral aRMM materials (which were distributed starting September 2020), in comparison to the approximate 6-7 month uptake of the

2019 Article 20 referral aRMM materials allowed for Sweden (which were distributed starting March 2020).

• **Reporting Period 3,** which will cover the 39-month period *after* the period of initial distribution and uptake of the 2019 Article 20 referral aRMM materials (1 October 2020 through 31 December 2023).

See Figure 2 for an overview of the VTE Reporting Periods 1-3.

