Age at tofacitinib initiation	Demographic	Calculated as the date of tofacitinib initiation minus the patient's year of birth and reported in the following categories: <18 years, 18-29 years, 30-39 years; 40- 49 years; 50-59 years; 60-69 years; 70-79 years; and $\geq$ 80 years; and <65 years and $\geq$ 65 years.		
Sex	Demographic	Reported in the following categories: Male, Female, and Unknown. Assessed on the date of the index tofacitinib prescription dispensing.		

 Table 3.
 Operational definitions of study variables in the selected databases

m In GKV claims, outpatient diagnoses are reported quarterly.

n In the PHARMO Database Network, the high-budget impact medication dataset contains only declared medication for approved indications. It might not be possible to determine off-label use in this dataset.

Variable	Role	Operational definition
Hepatic impairment	Comorbidity	Defined as ≥1 ICD-10 diagnosis code for hepatic impairment.
Hepatic impairment, mild or moderate o	Comorbidity	Defined as ≥1 ICD-10 diagnosis code for mild or moderate hepatic impairment.
Hepatic impairment, severe o	Comorbidity	Defined as ≥1 ICD-10 diagnosis code for severe hepatic impairment.
Renal impairment	Comorbidity	Defined as ≥1 ICD-10 diagnosis code for renal impairment or a combination of ICD-10 diagnosis codes and/or ICD-10 procedure codes.
Renal impairment, mild o	Comorbidity	Defined as ≥1 ICD-10 diagnosis code for mild renal impairment or a combination of ICD-10 diagnosis codes and/or ICD- 10 procedure codes.
Renal impairment, moderate o	Comorbidity	Defined as ≥1 ICD-10 diagnosis code for moderate renal impairment or a combination of ICD-10 diagnosis codes and/or ICD-10 procedure codes.
Renal impairment, severe o	Comorbidity	Defined as ≥1 ICD-10 diagnosis code for severe renal impairment or a combination of ICD-10 diagnosis codes and/or ICD- 10 procedure codes.
Herpes zoster (HZ)	Comorbidity	Defined as $\geq 1$ ICD-10 diagnosis code for HZ.
Human immunodeficiency virus (HIV)	Comorbidity	Defined as ≥1 ICD-10 diagnosis code for HIV.
Tuberculosis (TB), including both active and latent TB p	Comorbidity	Defined as ≥1 ICD-10 diagnosis code for TB.
Viral hepatitis B or C	Comorbidity	Defined as ≥1 ICD-10 diagnosis code for viral hepatitis B or C.

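### Age taken from year of birth classes about half of 64-year-old initiators as 65 or older and leaves the 65.5-year cut-off undefined

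*Protocol*

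**What the plan says.** Table 3 in protocol section 9.3.2 gives one age rule for all four countries: "Calculated as the date of tofacitinib initiation minus the patient's year of birth", with a split at 65. It repeats the rule for the elderly factor among the CV risk factors and again among the malignancy risk factors. No month, day or anchor within the birth year is given.

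Other rows rely on age at initiation and offer no other calculation:

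- The VTE age factor is "Defined as age at tofacitinib initiation >50 years".
- The outcome on initiation without a prior biologic is "Defined as patients who are 65 years and older on the date of the index tofacitinib" dispensing.

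The three turn-65 outcomes (discontinuation, inappropriate continuation, appropriate continuation) look at dispensings "from the time they turn 65.5 years old through to the end of the follow-up period". The stated reason is a grace period: "Patients have 6 months to discontinue tofacitinib to allow them time to be seen by their healthcare provider". These rows do not say how the 65.5-year date is obtained and do not refer to the year-of-birth rule.

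The data source descriptions (sections 9.4.1 to 9.4.4) list age without saying how finely birth date is supplied. Section 9.9 does not mention age derived from year of birth.

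**The concern.** Subtracting a birth year from a date makes anyone who starts before that year's birthday too old by up to a year. A patient born in December 1955 who starts in January 2020 is 64 but is classed as 65.

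Age 65 is the boundary of a restriction that came out of both the 2019 referral and the 2021 signal procedure (section 7). It feeds a primary compliance objective and a secondary objective on change over time (section 8). Patients below the boundary would be counted in the restricted age group, and a larger sample does not remove the error.

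The 65.5-year outcomes depend on the boundary more directly. Year of birth locates a birthday only to within 12 months, while the rule works in half-years.

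**Working it through.** The protocol states no figure for age misclassification, so there is none to reproduce.

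**Inputs.** From the protocol: the year-of-birth rule, the 65, >50 and 65.5 thresholds, the 6-month grace, and an indexing period that "will begin 01 April 2017 (i.e., the earliest date of the full distribution of the original aRMM materials for a country and indication") and ends 31 December 2023. Assumed: birthdays and index dates uniform over the year; 2-3% of initiators in each single year of age near 65; 20-40% of initiators truly 65 or older.

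**1. The 65 threshold, literal reading** (calendar-year difference, or age counted from 1 January of the birth year). Let u be the fraction of the year elapsed at the index date. A 64-year-old is classed as 65 when the birthday falls later that year, with probability 1 - u.

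- Whole years: the average of 1 - u over 0 to 1 is 0.50.
- Actual indexing period (6.75 years, of which April to December 2017 has mean 1 - u of 0.375): (6 x 0.50 + 0.75 x 0.375) / 6.75 = 0.486.
- By mid-month of initiation: about 96% in January, 46% in July, 4% in December.
- True 65-year-olds classed as under 65: 0%.

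**2. Other anchors** (simulation of 3 million patients, whole calendar years).

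| Anchor | 64 classed as >=65 | 65 classed as <65 |
|---|---|---|
| 1 January or year difference | 50% | 0% |
| 1 July | 12.5% | 12.5% |
| 31 December | 0% | 50% |

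**3. Effect on the >=65 share.** Excess = 0.5 x share of initiators aged 64.

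- 0.5 x 2% = 1.0 point; 0.5 x 3% = 1.5 points.
- Fraction of the >=65 group who are really 64: lowest 1.0 / (40 + 1.0) = 2.4%; highest 1.5 / (20 + 1.5) = 7.0%.

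**4. The >50 VTE factor.** Under whole-year subtraction, half of true 50-year-olds have a year difference of 51 and are classed as over 50, by the same arithmetic as step 1. If age is instead continuous from 1 January, those wrongly classed are 49-year-olds. Only one of these readings can apply.

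**5. The 65.5-year date.** Whole-year subtraction never yields 65.5, so an anchor is needed.

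- 1 January anchor: the cut-off is about 1 July of the year the patient turns 65. Those born from 2 July to 31 December (183 / 365 = 50.1%) reach it while still 64. The gap from 65th birthday to cut-off runs from -6 to +6 months, mean 0.
- 1 July anchor: none reach it before the birthday; the gap runs from 0 to 12 months, mean 6.
- 31 December anchor: none; the gap runs from 6 to 18 months, mean 12.

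**The case against.** **The 65.5 result is conditional.** A reader might infer that half of patients followed through 65 will reach the cut-off while still 64. The documents do not support that as fact, because those rows do not cite the year-of-birth rule. The share is 0% to 50% depending on the anchor. What stands is that year of birth alone cannot define the date, and no anchor is stated.

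**Compliance may not be biased in a known direction.** A reader might also infer that non-compliance is always overstated. For initiation at 65 or older without a prior biologic, the denominator is not explicit. If it is all patients classed as 65 or older, misclassified 64-year-olds enter numerator and denominator alike, and the bias depends on whether their biologic history differs. In the CV and malignancy composites, a 64-year-old with another listed factor is counted anyway. What is inflated is the >=65 group and the elderly factor itself.

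**Finer data are not shown.** The source descriptions list only age, so they do not establish that month or date of birth is available. The fix needs a fallback.

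**The effect is small.** An excess of 1.0-1.5 points compares with planned margins of 10 points at 97 patients and 5 points at 385 (section 9.5, Table 5). The same rule applies in every reporting period, so a similar error largely enters each side of a before-and-after description. This is a fair reason to keep the point modest.

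**The analysis plan could settle the anchor.** Section 9.3.2 says algorithms and code lists will be refined there. However, Table 3 openly defers the discontinuation windows, and sections 9.3.3 and 9.3.4 defer details of duration and dose. The age rows state a formula and defer nothing.

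**Conclusion.** The point holds in limited form. Table 3 fixes an age rule that, followed literally, classes about 50% of true 64-year-olds as 65 or older (48.6% over the actual indexing period) and makes no error the other way. This rests on uniform birthdays and index dates. The resulting excess in the >=65 share is about 1.0-1.5 points if each year of age near 65 holds 2-3% of initiators, a figure the protocol does not give. Under whole-year subtraction the >50 VTE factor is inflated in the same way.

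The 65.5-year date is undefined as written. If it follows the same 1 January reading, up to half of patients pass it before turning 65 and mean grace is 0 instead of 6 months. The protocol does not say that it does. The fault is worth correcting because it lies at the age threshold the study is meant to assess and is cheap to remove, not because it would overturn the overall proportions.

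**What to change.** In Table 3, calculate age from date of birth, or month and year of birth, or use the source's own age at the dispensing date, wherever the source supplies it. Use the same basis for the 50, 65 and 65.5 thresholds.

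Where only year of birth is available, anchor at 1 July for all three. This leaves 12.5% of 64-year-olds classed upward, offset by 12.5% of 65-year-olds classed downward, and restores the mean grace to 6 months. State the limitation in section 9.9.

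Add a sensitivity analysis that excludes patients whose index year minus birth year equals the threshold (65, or for the VTE factor the difference at which a patient first counts as over 50). Do not remove these patients from the main restricted-use count: on the uniform assumption, about half of those with a difference of 65 are truly 65.

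The cost is a few lines in Table 3 and section 9.9, one item in the data requests, and one small extra analysis in any source limited to birth year.
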